10 EVALUATIONS BY VISIT

10.1 Screening and Enrollment Visit (Day 0)

- Review the study with the subject and obtain written informed consent
- Assign the subject a unique subject number.
- Record demographics data.
- Record relevant medical history.
- Record concomitant medications.
- Perform a complete physical examination.
- Perform a complete review of systems including symptoms of postural dizziness
- Perform and record vital signs.
- Perform and record oximetry on room air and on current oxygen-delivering device.
- Perform and record results of blood pressure testing, including orthostatic vital signs.
- Document and review bloodwork obtained from standard clinical care (chemistry, hematology, hepatic function).
- Collect blood sample for research laboratory test(s): Biomarkers. Collect information on QTc if an electrocardiogram is performed per routine clinical care.
- Document and review chest imaging findings if performed per routine clinical care.

Version #: 2.8 Version Date: 11/6/2020 Page 15 of 30

10.2 Visit 1 (Day 1)

- First dose of Maraviroc Administered in morning. Study member will be present for first administration
- Perform interview with patient. Document any Adverse Events.
- Document complete physical exam.
- Perform and document medications review.
- Perform and record vital signs.
- Perform and record oximetry on room air and on current oxygen-delivering device.
- Record any events including transfer to intensive care, intubation, hospice referral.
- Document laboratory values and imaging obtained as part of routine standard of care.

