10.14 Early Withdrawal Visit (In-Hospital)

- Review and document Medication Administration Record.
- Perform and record vital signs, including orthostatic vital signs.
- Perform and record oximetry on room air and on current oxygen-delivering device.
- Document laboratory values and imaging obtained as part of routine standard of care.
- Assent to collect blood sample for clinical laboratory tests: Biomarkers at Day 3 and Day 7.
- Record any events including intubation, intensive-care admission, change to comfort measures, hospice referral or transfer.

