observed orthostasis is unlikely to be from Maraviroc given the low aforementioned incidence in Phase 3 trials. Furthermore, a study of orthostatic vital signs checked three times in one day in elderly patients admitted to the hospital (most commonly for stroke, infectious diseases, or other reasons) revealed that 2/3 of patients had one set of abnormal orthostatic vitals¹⁴. Therefore, we outline below dose-reduction and stop criteria per patient to address the risk for orthostasis.

Rates, severity, and relationship of postural dizziness, as well as exposure adjusted rates for orthostatic hypotension resulting in discontinuation, will be calculated at the point in which 10 patients have received more than four doses of treatment. The Medical Monitor may request trial stoppage in the instance that an unacceptable rate of discontinuation due to orthostatic hypotension reasonably attributable to Maraviroc is observed.

14.1.1 Dose reduction protocol:

All dose-reductions will be recorded in each subjects CFR.

Patients will be initiated on Maraviroc 300 mg twice daily. Orthostatic vitals will be obtained four hours after the first dose unless otherwise contra-indicated. If symptomatic and orthostatic, the next dose of Maraviroc can be held and inpatient team will be advised to review anti-hypertensive strategy, diuretic use and consider supplemental intravenous fluid if patient is anorexic and dehydrated. Subjects will be re-trialed on 300 mg of Maraviroc the next day. If still orthostatic, the patient will be re-trialed at 150 mg of Maraviroc the next day. Persistent orthostasis probably or definitely attributable (orthostasis that develops after starting Maraviroc that was not present at baseline) may prompt discontinuation of trial medicine with consideration of severity of orthostasis and after discussion with subject and inpatient care team. Withdrawing subjects will be asked to participate in a withdrawal visit as outlined above in section 10.14. Orthostatic vitals will be repeated during course of treatment at the discretion of inpatient care team.

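### Postural dizziness is asked about by name only before dosing, so the interim dizziness rate may run low; the Day 1 visit list also omits the four-hour orthostatic reading

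*Combined protocol and SAP*

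**What the plan says.** **Before dosing.** Section 10.1 (Day 0) has two specific items: "Perform a complete review of systems including symptoms of postural dizziness" and "Perform and record results of blood pressure testing, including orthostatic vital signs".

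**On treatment.** Section 10.2 (Day 1) opens with the first dose ("First dose of Maraviroc Administered in morning"). Its symptom prompt is "Perform interview with patient. Document any Adverse Events" and its blood pressure item is "Perform and record vital signs". Sections 10.3 to 10.9 (Visits 2 to 8) are equally general: none names dizziness or an orthostatic reading. Orthostatic vitals return only at the in-hospital early withdrawal visit (10.14): "Perform and record vital signs, including orthostatic vital signs".

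**What the safety section needs.** Section 14.1 commits to an interim calculation: "Rates, severity, and relationship of postural dizziness, as well as exposure adjusted rates for orthostatic hypotension resulting in discontinuation, will be calculated", once 10 patients have had more than four doses. Section 14.1.1 adds: "Orthostatic vitals will be obtained four hours after the first dose unless otherwise contra-indicated". Later orthostatic readings are left to the inpatient team. The dose-reduction steps begin when a subject is both symptomatic and orthostatic.

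**General ascertainment.** Section 9.1.8 requires adverse events to be elicited at each visit, by telephone first and in the room if the subject cannot use the telephone, with daily review of nursing documentation. Section 11.1 has the team probe for adverse events at each encounter. Neither names a symptom.

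**The concern.** Safety and tolerability are the chief interest of this trial, and there is no control arm. Postural dizziness is one of the few symptoms for which the protocol promises its own interim rate, and symptoms are half of the trigger for the dose-reduction steps. Section 14.1 itself cites the labelling advice that users on antihypertensives be asked about symptoms of orthostatic hypotension.

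The only named question falls before the drug is given. An open interview can miss mild or positional symptoms that a direct question would find, particularly in ill patients who are mostly in bed. With 8 or 10 subjects at the interim, one missed case moves the observed rate by 12.5 or 10 percentage points, and a low figure could be read as good tolerability when it partly reflects how the question was put.

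The four-hour reading is a second, separate matter. It is required by 14.1.1 but absent from the list that staff would follow on the day of the first dose. If it were overlooked, orthostatic hypotension could go undetected, with effects on dose reduction and discontinuation. It would not change the count of dizziness reports.

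**Working it through.** **1. Is the Day 1 list merely brief?** Sections 10.1 and 10.14 spell out orthostatic vitals in addition to, or as part of, vital signs. Section 10.2 lists plain vital signs on the first-dose day. The plain wording in 10.2 therefore cannot safely be read as including the four-hour reading. Section 10.2 is silent, however, and does not contradict 14.1.1. When the reading is placed in a visit list, one further point needs aligning: 8.1 has Day 0 extend to the first dose, while 10.2 puts that dose on Day 1.

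**2. The protocol's own benchmark.** Section 14.1 expects 6 to 8 patients with postural dizziness among 40 treated for 7 days, citing 14.1 (maraviroc) and 17.1 (placebo) per 100 patient-years.

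- Exposure: 40 × 7 / 365.25 = 0.767 patient-years.
- Expected patients: 0.767 × 0.141 = 0.11, and 0.767 × 0.171 = 0.13.

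The stated 6 to 8 is not reproduced. Reading the rates as percentages of 40 gives 5.6 to 6.8, and the crude 8% gives 3.2. The benchmark also uses 40 patients, while 16 are planned.

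**3. Illustration at the interim.** Let p be the true on-treatment risk, c the share of cases captured and n the number of subjects. The chance of recording no case is (1 − p × c)^n. Inputs:

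- n = 10 (14.1). The synopsis puts its interim analysis at 8, so both are shown.
- p = 8%: the crude Phase 3 figure in 14.1, from trials that 14.2 and 14.3 put at about 34 weeks. Applying it to 7 days is an assumption.
- p = 20%: 8 of 40 from 14.1. Step 2 shows that it does not follow from the cited rates, so it is only an illustrative upper value.
- c = 100%, 75% and 50%: assumptions, as the documents give no capture share.

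| n | Capture | No case if p = 8% | No case if p = 20% |
|---|---|---|---|
| 10 | 100% | 0.92^10 = 43% | 0.80^10 = 11% |
| 10 | 75% | 0.94^10 = 54% | 0.85^10 = 20% |
| 10 | 50% | 0.96^10 = 66% | 0.90^10 = 35% |
| 8 | 100% | 0.92^8 = 51% | 0.80^8 = 17% |
| 8 | 50% | 0.96^8 = 72% | 0.90^8 = 43% |

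Expected counts at n = 10 fall from 0.8 to 0.4 (p = 8%) or from 2.0 to 1.0 (p = 20%) when capture is halved.

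**4. The low end.** At 14.1 per 100 patient-years, the 7-day risk is 0.141 × 7 / 365.25 = 0.27%. At n = 10 the chance of no case is (1 − 0.0027)^10 = 97% with full capture and (1 − 0.00135)^10 = 99% with half. Capture then makes almost no difference. Section 14.1 expects these patients to be more prone to dizziness than that, because of illness and poor intake, but does not say by how much.

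**The case against.** The sponsor can fairly reply that the symptom is actively sought. Sections 9.1.8 and 11.1 require elicitation and probing, 9.1.8 adds daily nursing-note review and refers case-report-form recording to Section 14, and Section 14 lists postural dizziness first among its pre-defined events. Section 14.1.1 exempts only intubated and sedated subjects from monitoring for dizziness and orthostasis, which implies that others are monitored. All of this stands. It reduces the gap, but no on-treatment visit list carries the named question.

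Four stronger readings might be inferred, and the documents do not support them:

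- *Dizziness on drug is left to spontaneous mention.* The elicitation rules say otherwise. What can be said is that it is not asked about by name.
- *The four-hour reading is not planned, or 10.2 contradicts 14.1.1.* The reading is required by 14.1.1. Section 10 is not exhaustive: the repeat liver test for rash in 14.3 is in no visit list either.
- *The interim compares treatment with baseline and is biased toward no increase.* No such comparison of dizziness rates is planned. Baseline serves to attribute orthostasis in the individual subject.
- *The dizziness rate drives stopping.* The stated ground in 14.1 is an unacceptable rate of discontinuation for orthostatic hypotension, so missed mild dizziness would not enter that criterion directly.

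Open questioning is also a legitimate choice. A direct question will record more mild dizziness, some of it from the illness, and there is no comparator to separate the two.

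**Conclusion.** The point holds in limited form. A symptom whose rate is to be calculated at the interim, and which helps trigger dose reduction, is asked about by name only before treatment. Some on-treatment cases may therefore be missed and the dizziness rate may be too low. The missing four-hour item in 10.2 is a scheduling gap affecting detection of orthostatic hypotension.

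The size of any under-count cannot be derived. The table shows how far capture could matter if true risk were 8% to 20%; at the cited exposure-adjusted rate it would matter hardly at all. Both the risk range and the capture shares are assumptions. The point rests mainly on the mismatch between the visit lists and Section 14, and on how cheaply it can be closed.

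**What to change.** - Put the Day 0 postural-dizziness item, in the same words, into the daily interview at Visits 1 to 8, with four answers: yes, no, has not stood since the last visit, cannot answer.
- Calculate the 14.1 dizziness rate from that item among subjects able to answer, and report it beside the Day 0 response. This also settles the denominator for intubated and sedated subjects, on which the plan is silent.
- Reconcile the 10.2 visit list with 14.1.1 on the four-hour orthostatic reading, and align 8.1 with 10.2 on the day of the first dose.
- Reconcile the interim trigger: 10 patients in 14.1, but 8 in the synopsis and 14.3.

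The cost is one question in an interview already held each day, one case-report-form field and some text corrections. The drawback is a higher recorded rate of mild dizziness, part of it due to the illness and not the drug; showing the Day 0 response alongside helps the reader judge this.

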10.3 Visit 2 (Day 2)

- Review and document Medication Administration Record for Day 1 of study.
- Perform interview with patient. Record any Adverse Events.
- Document complete physical exam.
- Perform and record vital signs.
- Perform and record oximetry on room air and on current oxygen-delivering device.
- Record any events including transfer to intensive care, intubation, hospice referral.
- Document laboratory values and imaging obtained as part of routine standard of care.

10.4 Visit 3 (Day 3)

- Review and document Medication Administration Record for Day 2 of study.
- Perform interview with patient. Record any Adverse Events.
- Document complete physical exam.
- Perform and record vital signs.
- Perform and record oximetry on room air and on current oxygen-delivering device.
- Record any events including transfer to intensive care, intubation, hospice referral.
- Document laboratory values and imaging obtained as part of routine standard of care.
- Collect blood sample for research laboratory test(s): Biomarkers.

Version #: 2.8 Version Date: 11/6/2020 Page 16 of 30

10.5 Visit 4 (Day 4)

- Review and document Medication Administration Record for Day 3 of study.
- Perform interview with patient. Record any Adverse Events.
- Document complete physical exam.
- Perform and record vital signs.
- Perform and record oximetry on room air and on current oxygen-delivering device.
- Record any events including transfer to intensive care, intubation, hospice referral.
- Document laboratory values and imaging obtained as part of routine standard of care.

10.6 Visit 5 (Day 5)

- Review and document Medication Administration Record for Day 4 of study.
- Perform interview with patient. Record any Adverse Events.
- Document complete physical exam.
- Perform and record vital signs.
- Perform and record oximetry on room air and on current oxygen-delivering device.
- Record any events including transfer to intensive care, intubation, hospice referral.
- Document laboratory values and imaging obtained as part of routine standard of care.

10.7 Visit 6 (Day 6)

- Review and document Medication Administration Record for Day 5 of study.
- Perform interview with patient. Record any Adverse Events.
- Document complete physical exam.
- Perform and record vital signs.
- Perform and record oximetry on room air and on current oxygen-delivering device.
- Record any events including transfer to intensive care, intubation, hospice referral.
- Document laboratory values and imaging obtained as part of routine standard of care.

10.8 Visit 7 (Day 7)

- Review and document Medication Administration Record for Day 6 of study.
- Perform interview with patient. Record any Adverse Events.
- Document complete physical exam.

Version #: 2.8 Version Date: 11/6/2020 Page 17 of 30

- Perform and record vital signs
- Perform and record oximetry on room air and on current oxygen-delivering device.
- Record any events including transfer to intensive care, intubation, hospice referral.
- Document laboratory values and imaging obtained as part of routine standard of care.
- Collect blood sample for research laboratory test(s): Biomarkers

10.9 Visit 8 (Day 8)

- Review and document Medication Administration Record for Day 7 of study.
- Perform interview with patient. Record any Adverse Events.
- Document complete physical exam.
- Perform and record vital signs
- Perform and record oximetry on room air and on current oxygen-delivering device.
- Record any events including transfer to intensive care, intubation, hospice referral.
- Document laboratory values and imaging obtained as part of routine standard of care.

10.10 Post-Intervention Follow-up (Day 9 and every third day prior to discharge)

- Perform interview with patient. Record any Adverse Events.
- Perform and record vital signs.
- Perform and record oximetry on room air and on current oxygen-delivering device.
- Record any events including hospitalization, intubation, intensive-care admission.
- Document laboratory values and imaging obtained as part of routine standard of care.
- Obtain blood samples for research laboratory test on Day 15

10.11 Day of Discharge

- Perform interview with patient. Record any Adverse Events.
- Perform and record vital signs.
- Perform and record oximetry on room air and on current oxygen-delivering device.
- Document laboratory values and imaging obtained as part of routine standard of care.
- Record discharge destination, oxygen requirement at time of discharge.
- Obtain research labwork if discharge occurs earlier than Day 15

Version #: 2.8 Version Date: 11/6/2020 Page 18 of 30

• Schedule post-discharge phone follow-up.

10.12 Post-Discharge Follow-up (perform weekly till Day 35)

- Perform phone interview with patient. Record any Adverse Events.
- Review and document home medications.
- Review and document patient acquired vitals.
- Record any events including hospitalization, intubation, intensive-care admission.

10.13 Final Visit (Day 35)

- Inform subject this will be the final visit of the study.
- Perform interview with patient. Record any Adverse Events.
- If in hospital, record findings from abbreviated physical examination.
- If in hospital, perform and record vital signs.
- If in hospital, perform and record oximetry on room air and on current oxygendelivering device.
- If in hospital, document laboratory values and imaging obtained as part of routine standard of care.
- If in hospital, record any events including intubation, intensive-care admission, change to comfort measures, hospice referral or transfer.

10.14 Early Withdrawal Visit (In-Hospital)

- Review and document Medication Administration Record.
- Perform and record vital signs, including orthostatic vital signs.
- Perform and record oximetry on room air and on current oxygen-delivering device.
- Document laboratory values and imaging obtained as part of routine standard of care.
- Assent to collect blood sample for clinical laboratory tests: Biomarkers at Day 3 and Day 7.
- Record any events including intubation, intensive-care admission, change to comfort measures, hospice referral or transfer.

10.15 Early Withdrawal Visit (Out-of-Hospital)

- Review and document home medications.
- Review and document patient acquired vitals.
- Document subjects' current location of care type (e.g. acute rehabilitation center).

Version #: 2.8 Version Date: 11/6/2020 Page 19 of 30

• Record any events including intubation, intensive-care admission, change to comfort measures, change to do not hospitalize (DNH), hospice referral or transfer.

10.16 Death

- If in hospital, review and document Medication Administration Record. Document laboratory values and imaging obtained as part of routine standard of care.
- Review and document time and cause of death.
- Inform IRB of subject death.
- Record any preceding events including hospitalization, intubation, intensive-care admission, change to comfort measures, hospice referral or transfer.

11 ADVERSE EXPERIENCE REPORTING AND DOCUMENTATION

11.1 Adverse Events

An adverse event (AE) is any untoward medical occurrence in a clinical investigation of a patient administered a pharmaceutical product and does not necessarily have a causal relationship with the treatment. An AE is therefore any unfavorable and unintended sign (including an abnormal laboratory finding), symptom or disease temporally associated with the administration of an investigational product, whether or not it is related to that investigational product. An unexpected AE is one of a type not identified in nature, severity, or frequency in the current Investigator's Brochure or of greater severity or frequency than expected based on the information in the Investigator's Brochure.

The study team will probe, via discussion with the subject, for the occurrence of AEs during each subject encounter and record the information in the site's source documents. Adverse events will be recorded in the patient case-report form. Adverse events will be described by duration (start and stop dates and times), severity, outcome, treatment, and relation to study drug, or if unrelated, the cause.

AE Severity

The National Cancer Institute's Common Terminology Criteria for Adverse Events (CTCAE) Version 4.0 should be used to assess and grade AE severity, including laboratory abnormalities judged to be clinically significant. Only for the specific Adverse Event of change in liver enzymes will The National Cancer Institute's Common Terminology Criteria for Adverse Events (CTCAE) Version 5.0 be used. If the experience is not covered in the modified criteria, the guidelines shown in Table 2 below should be used to grade severity. It should be pointed out that the term "severe" is a measure of intensity and that a severe AE is not necessarily serious.

Version #: 2.8 Version Date: 11/6/2020 Page 20 of 30

Table 2. AE Severity Grading

Severity (Toxicity Grade)	Description
Mild (1)	Transient or mild discomfort; no limitation in activity; no medical intervention or therapy required. The subject may be aware of the sign or symptom but tolerates it reasonably well.
Moderate (2)	Mild to moderate limitation in activity, no or minimal medical intervention/therapy required.
Severe (3)	Marked limitation in activity, medical intervention/therapy required, hospitalizations possible.
Life-threatening (4)	The subject is at risk of death due to the adverse experience as it occurred. This does not refer to an experience that hypothetically might have caused death if it were more severe.

AE Relationship to Study Drug

The relationship of an AE to the study drug should be assessed using the following the guidelines in Table 3. In delineating AE relationship, research team will consider adverse events temporally or otherwise clearly related to administration of the drug in relation to noted deviation from natural history of SARS-CoV-2 infection.

Table 3. AE Relationship to Study Drug

Relationship to Drug	Comment
Definitely	Previously known toxicity of agent; or an event that follows a reasonable temporal sequence from administration of the drug; that follows a known or expected response pattern to the suspected drug; that is confirmed by stopping or reducing the dosage of the drug; and that is not explained by any other reasonable hypothesis.
Probably	An event that follows a reasonable temporal sequence from administration of the drug; that follows a known or expected response pattern to the suspected drug; that is confirmed by stopping or reducing the dosage of the drug; and that is unlikely to be explained by the known characteristics of the subject's clinical state or by other interventions.
Possibly	An event that follows a reasonable temporal sequence from administration of the drug; that follows a known or expected response pattern to that suspected drug; but that could readily have been produced by a number of other factors.
Unrelated	An event that can be determined with certainty to have no relationship to the study drug.

